## 6.5 RECRUITMENT AND SELECTION OF PARTICIPANTS

The study will be advertised through the distribution of flyers from Cana Farm and Cana Communities personnel and through the Cana Communities monthly newsletter. Posters will also be placed across Cana Communities sites across New South Wales. Permission will be obtained from each of these sites prior to advertising the study.

All advertising material will have the contact number and email address of our research team included, and interested participants will contact us directly if they wish to hear more about the study. Alternatively, interested participants can speak to staff at Cana Communities sites and Cana Farm directly for more information about the study, as well as provide verbal consent for staff to provide the research staff with their contact details.

We will avoid real or perceived coercion by indicating in the recruitment flyers and posters that the study is completely voluntary. The Participant Information Sheet will outline that participants can withdraw from the study at any time, and that this will not influence their relationship with Cana Communities, Cana Farm, their own health care providers or health care services in the community, the University of Sydney or the University of New South Wales.

### 6.5.1 INCLUSION AND EXCLUSION CRITERIA

**Inclusion criteria:**

We will recruit individuals aged 18 years and over who express interest in the CanaCare study.

**Exclusionary criteria:**

Participants who present with active suicidal ideation, active psychosis, delirium, acute withdrawal or unstable cardiovascular or other disease will be referred for appropriate treatment, and may be eligible to enrol in the study upon completion of appropriate treatment.

Participants will be excluded if they have a rapidly progressive or terminal illness.

**6.5.2 INTERVENTIONS**

Below is a description of person-centred care and of each health professional's scope of practice and role within the CanaCare study.

**Person-centred care (PCC):**

Traditional models of care (TMC) have often been described as deficit or illness-based models, where primacy is given to the illness, symptom or impairment. The overarching emphasis is on curing or managing the conditions, and the individual often plays a passive role in planning. TMC within the mental health sector, has predominantly seen participation in one's community and personal choice often as the 'reward' to compliance with treatment, and symptom reductions.

Person-centred care differs in that it provides participants with the choice of the services they use, and encourages an active or self-directed role. Participants are included in the clinical team, and have discretion to invite family members and other support persons to be involved.

**Physician:**

The study director/study physician will have overall responsibility for the medical assessment and health and wellness programming offered to each participant. She will undertake a medical history and physical examination at the first assessment when the participant comes to the CanaCare clinic at the University of Sydney or a thorough medical history via a secure online platform. If the latter is performed, a physical examination will be conducted at a later date that is mutually agreed upon and complies with the Department of Health COVID-19 recommendations. Based on this assessment and the person's goals, she will recommend additional assessments which will be performed by the clinic staff. Subsequently, after a case conference is held to review all results, specific elements of the wellness program will be prescribed to be implemented by the clinic staff in collaboration with the participant. These may include nutritional, exercise, and other behavioural strategies to be carried out under supervision or independently, as deemed appropriate and most feasible for each individual. She will not take over the chronic medical care of the participant, but with permission may communicate findings from the assessments to the GP/primary community health care team for ongoing treatment of identified medical conditions or need for further testing. The physician will also have responsibility for adjudicating all adverse events as related to the study or not, and reporting of these adverse events to other health care professionals and the HREC as required.

**Dietetics:**

Accredited practising dietitians (APDs) have undergone tertiary level training to provide expert nutrition and dietary advice to both individuals and groups on nutritional related matters (Dietitians Association of Australia [DAA], 2015). APDs within the CanaCare team will conduct assessments, perform diagnoses, implement interventions, as well as monitor and evaluate the therapeutic plan (DAA, 2018). They may provide education around healthy eating, shopping, and cooking, weight loss/weight gain, health with the management of a chronic health condition/s related to dietary patterns, and safe use of alcohol.

When working with individuals who have a mental health condition, APDs will utilise client-centred strategies for long-term dietetic and life-style self-management of relevant physical health outcomes, including goals related to long-term medication use (DAA, 2018).

**Exercise Physiology:**

Accredited exercise physiologists (AEPs) have tertiary level training with the knowledge and skills to design, deliver and evaluate safe and effective exercise interventions for individuals who may have acute, sub-acute or chronic medical conditions, injuries or disabilities (Exercise & Sport Science Australia [ESSA], 2018). The overall aim of the AEP is to prevent, manage and assist individuals to regaining their optimal physical function, health or wellness (ESSA, 2018). If participants elect to see an AEP or exercise scientist, they will design an exercise intervention to improve strength and/or fitness, improve balance and reduce the risk of falls, improve body composition (decreasing fat mass and increasing muscle mass and increasing bone density), and better manage any chronic health condition/s they may have.

**Psychology:**

Psychology is defined as the study of behaviour and mind (American Psychological Association, 2019d). A psychologists' role is to understand the behaviour of an individual, and are trained to understand how the mind works. Individuals have multiple complexities and factors such as personality, developmental milestones, societal and cultural factors need to be taken into consideration. The psychologist's role is to take in and understand these complexities of a person to provide assessment and intervention according to the individual. The psychologists on the CanaCare team will assist individuals who may have been feeling depressed, angry, anxious, social isolation, fatigue or insomnia. Those who require support for managing a chronic health condition, coping strategies to use in stressful situations, overcoming substance-use disorders, or re-integration into family and social relationships.

**Social Work:**

Social work is committed to human rights and social justice and the relationship of these issues to health care and wellbeing. Social workers can support individuals, families, groups and communities within the contact of their social, physical and cultural environment, acknowledging their current and previous experiences, as well as their cultural and belief systems (Australian Association of Social Workers, 2019). The social worker on the CanaCare team will assist individuals on many of the issues listed above in psychology, as well as assisting in finding suitable accommodation, employment and educational opportunities.

**Pharmacy:**

A pharmacist can provide education, counselling around medications and conditions, as well as perform a medication review to optimise the benefits/side effects/drug interactions related to the participant's medication regime in collaboration with a physician. The pharmacist

within the CanaCare team will support participants by reviewing medication regimes with the participant and study physician, assist with adherence of prescribed medications, and provide education about medications and of drug-drug and drug-nutrient interactions and how they affect the health status of the participant.

### **Physiotherapy:**

A registered physiotherapist has completed tertiary level training to assess, diagnose and treat/manage individuals with pain and problems with movement caused by joint, muscles and nerve disorders. Physiotherapists on the CanaCare team will assess the participant, consider their values, take note of their history (medical, psychological, social and cultural aspects) and will conduct an appropriate physical examination - where relevant - to design a suitable treatment plan. This may include providing treatment, advice, prescribing an exercise/mobility/balance program and liaising with other health practitioners, such as exercise physiologists to optimise exercise prescription.

## **7. ETHICAL CONSIDERATIONS**

### **7.1 ETHICS APPROVAL**

Ethics approval will be sought from the University of Sydney Human Research Ethics Committee only.

### **7.2 INFORMED CONSENT PROCESS**

During each stage of the screening process, participants will be informed of the purpose of the screening, and what will happen to their data.

Participants will be provided with a Participant Information Statement (PIS), outlining all the procedures of the study, and what their participation will involve. The PIS will outline any potential risks, and benefits of the study. Participants will be made aware that participation is voluntary, and that they are free to withdraw at any time, without any effect on their relationship with Cana Communities, Cana Farm, the University of Sydney, the University of New South Wales or any investigators in the study.

A research assistant will read the PIS with the participant and with their Cana Support Person present. They will provide participants with the opportunity to ask questions, and discuss the study in greater detail. Participants will consent to the study by signing the Participant Consent Form. The Cana Support Person will sign as the witness to the signature.

### **7.3 CONFIDENTIALITY AND PRIVACY**

Data will be collected both in person and over the phone or by videoconferencing (University Zoom account) as needed at various times during the study. The data will be entered into the secure REDCAP database and [name] secure USYD data server. Whenever a Zoom meeting is used a password will be sent to the participant/s and meeting details only available to research personnel and the participant/s being interviewed. If a Zoom meeting needs to be recorded so that the data can be extracted later or shared with another research personnel, the resulting file containing the information will be saved to an encrypted local drive (ie., a laptop or a desktop drive, not a removable media such as a USB or removable hard drive). Any such recording will be removed to [name] RDS as soon as possible and deleted from the local drive. Data gathered from the physician screening, case conference, assessments, intervention, planning and delivery will be entered by the research

staff into a database created in REDCAP and will also be stored in a secure, University of Sydney server and will be password protected. Data will be entered using a re-identifiable form using unique identity numbers. The code will be used on all electronic data forms, electronic databases and hard copy forms. No forms will contain the names of the participants, or other identifying information. Data gathered from the physician screening, case conferences, assessments, intervention planning and delivery will be entered by the research staff into a database created in REDCAP and will also be stored on a secure, University of Sydney server, and will be password protected. Data will be entered in a re-identifiable form using unique identity numbers. This code will be used on all electronic data forms, electronic databases and hard copy data forms. No forms will contain the names of participants, or other identifying information.

All participant information will remain re-identifiable, so that information that is relevant to their medical care can be communicated to appropriate medical professionals. Participants will only remain re-identifiable to persons directly involved with the study, namely the Primary and Associate Investigators, and Research Assistants or HDR students who are conducting the intervention/assessments.

All data will be de-identified prior to depositing in a repository at the end of the study, as required by the National Health and Medical Research Council.

## **8. SAFETY CONSIDERATIONS**

### **8.1 ADVERSE EVENTS**

Adverse events will be monitored through the administration of a weekly questionnaire and reporting of events throughout the study period. If participants report any adverse events, these will be reported to the University of Sydney HREC. These will be reported even if they may be unrelated to the intervention, this will be adjudicated by the study physician.

Serious adverse events resulting in hospitalisation or death will be reported to the University of Sydney HREC within 24 hours, whether or not they may be unrelated to the intervention. In both cases, participants will be followed-up by phone or in-person until resolution of the adverse event.

### **8.2 RISKS OF THE STUDY**

Outlined below are possible risks associated with different assessments and interventions.

#### *Self-reported/practitioner-administered questionnaires:*

Fatigue and psychological distress may accompany testing. This will be minimised by frequent breaks as needed, and highly experienced allied health professionals and research staff conducting the testing. Questionnaires will be performed confidentially in a private area with the participant, Cana Support person and researcher/practitioner present.

### *Muscle soreness and injury:*

As with any exercise testing or training, there are possible risks of injury or a heart attack. Participants will undergo a physician screen prior to any testing procedures being conducted, and medical information will be sought after from the participants GP and/or specialists when necessary to ensure there is no contraindication to exercise testing or training.

The exercise testing may cause some muscle soreness and fatigue. There is also a small risk of musculoskeletal soreness or injury during physical function tests, however, this is very rare during the kind of strength, balance, functional mobility and gait testing proposed here. Participants will be closely supervised by a trained and experienced health professional during all testing procedures. To minimise these risks, we will carefully monitor participants throughout the testing to maximise their safety. Adverse events during testing will be immediately reported to the study physician, who will take care of those participants suffering from harm related to participation in the study.

To reduce the chance of adverse events during the exercise sessions, each session will start with asking participants how they feel and if there has been any changes to their medical health. Participants will be asked to complete a weekly health check report in which they should indicate if there has been: no special events, worsening of disease, newly diagnosed disease, or if they have been in the hospital. In addition, participants will be asked to classify the cause of the event to different diseases/incidents.

Exercise sessions will be supervised, either directly or remotely, by an experienced health professional. Supervised sessions can be performed in a one-to-one session or in small groups to allow close supervision of each participant. Exercise intensity will be monitored throughout all training sessions via continuous monitoring of rate of perceived exertion, heart rate (aerobic exercise) and close monitoring of signs and symptoms. The exercise session will be terminated prematurely if a participant shows signs of any discomfort. Any events/episode during the exercise session will be followed-up by the study physician.

### *Radiation:*

This research study may involve exposure to a very low amount of radiation from dual X-ray absorptiometry (DXA) scanning for body composition assessment when this is indicated for particular participants. The effective dose of radiation from this study is very low at about 0.06 millisieverts (mSv) over the 12-month period. For comparison, everyone receives a dose of about 2 mSv each year from natural sources as part of everyday living, so the study is equivalent to a few days of natural "background" radiation. No harmful effects have been demonstrated at this level and the risk is minimal. Participants are advised to inform the researchers if they have participated in any research study in the last five years where they were exposed to radiation. Participants are also advised to show the participant information statement to the research staff if any other studies they choose to volunteer for in the next 5 years.

### *Adverse Effects:*

During each test procedure, and at regular intervals throughout the program, we will ask participants to inform us of any side effects that they may experience. Participants will be

advised that they must contact the study staff immediately if there are any unusual health experiences, injury or bad effects. This notification should take place whether or not they believe that the problem is related to the program or from some other cause. Prior to any testing, the study physician will review participant's medical history to make sure they are medically ready for the study procedures.

In the event of an injury or other misadventure, we will contact the participant's GP, and may recommend an appropriate course of action in consultation with the GP as necessary. In the event of any adverse effect participants will be able to contact the study physician [name] [name] on [name].

## 9. OUTCOMES

Table 1 illustrates the CanaCare Clinic primary and secondary outcomes. All participants will complete the Oxford Happiness Questionnaire. Other outcome measures will be completed if they are relevant to the participant's goals.

Table 1. CanaCare Primary and Secondary Outcomes.

Primary Outcomes
1. Oxford Happiness Questionnaire score
Secondary Outcomes
1. Neuropsychological Outcomes 
 
1.1. Self-efficacy 
 
1.1.1. Ewart's Self Efficacy Scale
 
 
 
1.2. Empathy 
 
1.2.1. Toronto Empathy Scale
 
 
 
1.3. Quality of Life 
 
1.3.1. Short Form 36 Health Survey Questionnaire (SF-36)
 
 
 
1.4. Depression 
 
1.4.1. Patient Health Questionnaire-9 (PHQ-9)
 
1.4.2. Hamilton Depression Rating Scale (HAM-D)
 
 
 
1.5. Anxiety 
 
1.5.1. Generalised Anxiety Disorder 7-Item (GAD-7)
 
 
 
1.6. Post-traumatic Stress Disorder Symptoms 
 
1.6.1. Post-traumatic Stress Disorder Symptom Scale – Interview for DSM-5 (PSS-I-5)
 
 
 
1.7. Mindfulness 
 
1.7.1. Mindfulness Attention Awareness Scale
 
 
 
1.8. Experiential Avoidance 
 
1.8.1. Acceptance and Action Questionnaire (AAQ)
 
 
 

2. Aerobic Capacity 
 
2.1. Maximal aerobic capacity (VO2peak) 
 
2.1.1. Graded treadmill test to voluntary fatigue with indirect calorimetry
 
 
 

3. Muscular Strength 
 
3.1. One Repetition Maximum (1RM) (seated leg press, unilateral knee extension, chest press, and seated row)
 

4. Nutrition 
 
4.1. Short Form Food Frequency Questionnaire (SFFFQ)
 
4.2. CanaCare Dietary Questionnaire
 

5. Physical Performance 
 
5.1. 6-minute Walk Test (6MWT)
 
5.2. Short Physical Performance Battery
 
5.3. Balance (static and dynamic)
 


6. Anthropometry
 
6.1. Waist, upper-arm and calf circumference (cm)
 
6.2. Height (cm)
 
6.3. Weight (kg)

7. Body Composition
 
7.1. Whole body and regional lean and adipose tissue, Bone density in the lumbar spine and hip - Dual-energy X-ray absorptiometry (DXA)

8. Sleep Quality
 
8.1. Subjective sleep quality Pittsburgh Sleep Quality Index (PSQI)

9. Health Status
 
8.1 Past medical history Past medical diagnosis and symptoms (physical, mental or emotional), past treatments, medications, past falls.
 
8.2 Ongoing health status New medical diagnosis, new (or change) in symptoms, new (or change) in medications, falls, visits to health care practitioners. Gathered using a weekly health check questionnaire

10. Adherence to Intervention
 
10.1. All adverse events related and not related to the intervention. Gathered using weekly health status check and reporting of events throughout the study period.

11. Cognitive Function
 
11.1. Montreal Cognitive Assessment (MoCA) score

12. Haemodynamic Measures
 
12.1. Blood pressure Resting, orthostatic

13. Alcohol-related Outcomes
 
13.1. AUDIT-C

14. Physical Activity Levels
 
14.1. Subjective physical activity Paffenbarger Physical Activity Questionnaire Physical Activity Scale for the Elderly

15. Metabolic
 
15.1. The Australian Type 2 Diabetes Risk Assessment Tool (AUSRISK)

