#### **4. AIMS / OBJECTIVES / HYPOTHESES**

The primary aim of the CanaCare program is to utilise a person-centred approach to care planning and delivery, provided in collaboration with an interdisciplinary team with the overall aim of improving the health and wellness for all participants.

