##### **Primary Hypotheses**

Participation in the interdisciplinary CanaCare program, utilising a person-centred approach, will result in a significant improvement in the Oxford Happiness Score after 6 months.

Secondary aims of the study will be to assess the effect of the study on improvements in nutrition and health status, functional status, sleep quality, physical activity participation, neuropsychological outcomes (including depression, anxiety, self-esteem, and empathy), maximal aerobic capacity, muscle strength, physical performance, anthropometric parameters and body composition (including fat mass, fat free mass and bone mineral density).

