### **6.3 STUDY DESIGN**

Participants will be accompanied by a support person from the Cana Communities volunteer pool to the University of Sydney study site or will be supported by their support person to access one of the three online platforms (mentioned above) at a designated time. The participants will initially meet/talk to [name] [name] [study physician] to identify their primary goals/reasons for wanting to take part in the research program. Depending on what the participants identify as their primary (life) goal or aspiration/s, the physical and medical history assessment will focus on areas relevant to their goals.

Participants will then meet with one or more allied health practitioners for additional assessments to be completed. The interdisciplinary team will consist of accredited dietitians, accredited exercise physiologists, social workers, registered psychologists, registered physiotherapists and pharmacists. These assessments may include questionnaires, structured interviews, counselling sessions, body composition testing, nutritional assessments, fitness assessments and drug reviews.

A case conference will be held with all health practitioners involved in the participants' care. Subsequently, a case conference will be held with the team and the participants, with their support person present, to discuss their assessments, and how they relate to their goals. Through discussions with the participant, initial components of the Wellness program will be made. This may include exercise, dietary changes, mental health strategies such as mindfulness or meditation or cognitive behavioural therapy, or lessening of substance use, as appropriate. The care provided by CanaCare will be in addition to the usual supports provided by Cana Communities for effective reintegration into work, housing support, and social relationship building, among other offerings.

The Wellness program may take place across different sites including the University of Sydney Camperdown campus, Cana Communities sites around Sydney and Cana Farm in Orchard Hills and via the secure online platform chosen. Programs may be supervised or unsupervised, as appropriate, and will be interdisciplinary in nature. Where relevant, the study physician may make referrals to the participant's general practitioner, a psychiatrist or specialist.

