Each participant will be linked with a Cana Communities volunteer from the community who will be his/her primary coordinator of care, depending on the most important or urgent goal or wellness need identified. This person will be responsible for follow-up by telephone on a weekly basis initially, to assist with the adoption of the Wellness program elements.

Follow-up will be planned for 3 months and 6 months to re-evaluate and re-set goals (either in-person or online). The participant will be accompanied/supported by their Cana support person if needed.

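### Secondary outcomes are measured only where relevant to a participant's goals, goals are re-set at follow-up, and nothing requires a baseline measure to be repeated at 6 months

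*Protocol*

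**What the plan says.** Protocol Section 9 separates the primary outcome from the rest. For the primary: "All participants will complete the Oxford Happiness Questionnaire". For the others: "Other outcome measures will be completed if they are relevant to the participant's goals".

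Goals also steer the baseline work-up. In Section 6.3, "the physical and medical history assessment will focus on areas relevant to their goals". In Section 6.5.2, under the physician's role: "Based on this assessment and the person's goals, she will recommend additional assessments which will be performed by the clinic staff".

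Goals are not fixed. Section 6.3 states: "Follow-up will be planned for 3 months and 6 months to re-evaluate and re-set goals".

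The aims carry no matching restriction. Section 4 says: "Secondary aims of the study will be to assess the effect of the study on improvements in nutrition and health status, functional status", followed by a list of further domains, with no limit to participants whose goals make a domain relevant. The overall aim in the same section is framed "with the overall aim of improving the health and wellness for all participants". Section 6.4 analyses outcomes over time by repeated-measures ANCOVA with a main effect of time, at a 0.05 threshold. No comparison group is described.

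**The concern.** A before-after analysis needs the same measure on the same people at both times. The only collection rule for the scales, performance tests and body measures in Table 1 is relevance to goals, and goals may change. Three things follow if the rule is applied as written.

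- **Follow-up may depend on response.** A measure taken at baseline may lapse at 6 months because the goal was met or because it was given up.
- **Baselines may be missing.** A measure that becomes relevant at 3 months has no baseline value.
- **Entry may depend on the baseline level.** If people tend to choose goals where they score badly, regression to the mean looks like improvement, and there is no control group to subtract it.

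At stake is the meaning of most secondary results, which could be read as effects in the cohort when they describe a goal-selected subset. Who is measured, on what and when is settled by the protocol. A separate SAP cannot recover values that were never collected.

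**Working it through.** **1. The plan's own figure.** Section 6.2 gives 57 participants for a within-group change with g = 0.38, two-sided alpha 0.05 and power 0.80. The exact paired t-test (noncentral t) gives n = 57, with power 0.805. The figure reproduces, but it concerns the primary outcome, which everyone completes. No secondary outcome has a sample size claim.

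**2. Complete pairs under the goal rule.** The protocol gives neither the share measured at baseline nor the share still measured at 6 months, so both are assumed here. Pairs = 57 × share measured × share retained. Power is for a standardised change of 0.38.

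| Measured at baseline | Still measured at 6 months | Pairs | Power |
|---|---|---|---|
| 70% | 90% | 36 | 0.60 |
| 50% | 70% | 20 | 0.37 |
| 30% | 50% | 9 | 0.17 |

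This bears on precision only. It shows why n must accompany each secondary result.

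**3. Selection at follow-up.** The direction of bias is not determined. If measures lapse because goals were met, improvers are lost and change is understated. If they lapse because goals were given up, non-improvers are lost and change is overstated. The documents do not say which would dominate, so no figure is attached.

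**4. Selection at entry (regression to the mean).** Assume a normal score, no true effect, and correlation r between baseline and 6 months.

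- *Ceiling: selection on the observed baseline score itself.* Expected apparent change = (1 − r) × m, where m is the mean distance of the selected group from the cohort mean, in SD. For the worse half, m = 0.798. With r = 0.6: 0.4 × 0.798 = 0.32 SD. With r = 0.7: 0.3 × 0.798 = 0.24 SD.
- *Weaker link.* Suppose goal relevance correlates 0.5 with the baseline score and has no further link to the 6-month score. The expected change is multiplied by 0.5: 0.16 SD (r = 0.6) and 0.12 SD (r = 0.7).
- *Stable need.* If goals reflect only the stable part of a person's level, the selected group has the same expected score at both times, and the expected change is zero.

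The plausible range for the worse half is therefore 0 to about 0.32 SD. For scale, the primary planning effect is 0.38.

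**The case against.** The best defence is that goal-dependent assessment is an open choice that follows from person-centred care. Section 8.2 notes that questionnaires can bring fatigue and distress, so limiting them is reasonable. The hypothesis and the sample size rest on the primary outcome alone. This stands. It lowers the weight of the point and argues against a large battery for everyone.

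Several stronger readings are tempting but not supported:

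- **That the measured set does shift.** Section 6.3 says goals are re-set; it does not say that scales are dropped or added. The synopsis speaks of asking some social-status questions before and after, and a repeated-measures analysis presupposes repeated values. The defect is that repetition is not required, not that it is ruled out.
- **That only people with a problem in a domain are measured.** Section 6.3 speaks of life goals or aspirations, and the physician also recommends assessments. No rule selects on a poor score, and goals are discussed before the further assessments are done.
- **That the bias equals or exceeds the planning effect.** Selecting the worst quarter on the observed score (m = 1.271) would give 0.38 to 0.51 SD, but nothing in the protocol implies such selection. The worse-half ceiling stays below 0.38.
- **That participants outside a subset are not seen at all.** Everyone completes the primary questionnaire, and adverse events are monitored weekly (Section 8.1). Such participants are unobserved only on the particular scale.

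It is also fair to say that the sentence on secondary aims names no population; the reference to all participants is in the overall aim. The mismatch with Section 9 is one of unstated scope rather than flat contradiction.

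**Conclusion.** The point holds as a gap in the collection rule. Sections 6.3 and 9 together allow observation of a secondary outcome at 6 months to depend on what happened to the goal, and allow measures without a baseline. Sections 4 and 6.4 treat the secondary outcomes as if neither could happen.

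For the worse half with r of 0.6 to 0.7, the possible spurious improvement is at most about 0.24 to 0.32 SD, about half that under a 0.5 link, and near zero if goals reflect stable need. This rests on assumed normality, selected share, r and strength of the link between goals and score; the documents give none of these. Bias from goal-dependent follow-up could run either way.

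The primary outcome, adverse events and the weekly health check are not affected. Although the last two are listed among the secondary outcomes, Section 8 has them collected by weekly questionnaire throughout the study. The change should be made, but the main hypothesis does not depend on it.

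**What to change.** Amend Sections 6.3 and 9 as follows.

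1. Fix each participant's outcome set at baseline, and repeat every baseline measure at 6 months whatever happens to the goals. Goals may still be re-set to guide the programme.
2. Analyse change only for measures with a baseline value. A measure added later may be described but not analysed as change from baseline.
3. State secondary results as change among participants for whom the measure was goal-relevant, with n and 95% CI, and word the secondary aims in Section 4 to match.
4. Optionally, give one or two short questionnaires already in Table 1 to all participants at baseline and 6 months, so that at least some secondary results describe the whole cohort.

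No new instruments or visits are needed. The cost is some extra testing time and burden, including the fatigue or distress noted in Section 8.2, which is why the optional core should stay minimal. Step 1 removes loss of follow-up data caused by changed goals. It does not remove regression to the mean or loss through withdrawal; step 3 keeps the claim within what was measured.
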